- Trigger additional dose cohort(s) based on the safety/tolerability, PK and antitumor efficacy data.

When there are other patients that are ongoing at the time of this review, the SRC may decide to defer their decision until these further patients become evaluable.

Any patient started on treatment in error, as he/she failed to comply with all of the selection criteria but meets the criteria of an evaluable patient, will be reviewed on a case by case basis by the SRC to determine if the patient should be included or excluded for decision.

Definition of DLT-like event

Any toxicity not attributable to the disease or disease-related processes will be considered a DLT-like event if it occurs during Cycle 1 (first 21 days of repeated dosing of AZD4205) in dose escalation cohorts. DLT-like events will be defined as the following:

- > Hematological toxicity including:
 - CTCAE (version 5) Grade 4 or above present for more than 4 days
 - Febrile neutropenia
- > Non-hematologic toxicity including:
 - Grade 3 or 4 non-hematologic toxicity (excluding alopecia), that is dose limiting in the judgment of the investigators and the Medical Monitor/Study Physician
 - Grade 3 or 4 laboratory abnormalities which are not considered clinically significant and which resolve within 48 hours, will not be considered as a DLT
 - An increase in AST or ALT ≥ 3×ULN and total bilirubin ≥ 2×ULN where no other reason other than investigational treatment can be found to explain the combination of increase
 - Confirmed QTc prolongation (> 500 msec absolute or > 60 msec above baseline)
 - Decrease in lung function: either DLCO or FEV1% decrease to ≥ CTCAE Grade 3
 - LVEF decrease to < 40%; or LVEF [40 54%] and LVEF \geq 10% decrease from baseline; or any symptomatic LVEF decrease.
- Any other toxicity that:
 - is greater than baseline, is clinically significant and/or unacceptable, and is judged

to be a DLT-like event by the SRC

- that is a protocol defined stopping criteria (i.e. confirmed pneumonitis or life-threatening arrthymia)
- prevents completion of at least 80% of planned doses

Dose escalation scheme

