5.1.3 Dose modifications

5.1.3.1 Toxicity management and dose modifications to AZD4205

If a patient has a treatment emergent adverse event (TEAE) at least possibly related to AZD4205, then dose interruptions/holds with possible modifications as described in Table 1 should be implemented. Deviations from these guidelines may occur based on the clinical judgment of the investigator with notification to the Sponsor. For managing toxicity related to the eye, refer Appendix VII.

Table 1 Dose Interruptions/Modifications for Toxicities Observed in the Study

Category	Toxicities needing immediate interruption	Dose modification plan
	$\mathrm{ANC} < 0.5 \times 10^9/\mathrm{L}$	Immediate interruption of AZD4205. Once toxicity has resolved to recovery to ≤ Grade 2 or baseline within 14 days of onset: Resume at the same dose for the 1st occurrence of the event Resume at the reduced dose for the 2nd occurrence of the event Permanent discontinue for the 3rd occurrence of the event
Hematological	Platelet count $< 25 \times 10^9/L$	Immediate interruption of AZD4205 Once toxicity has resolved to recovery to ≤ Grade 2 or baseline within 21 days of onset: Resume at the same dose for the 1st occurrence of the event Resume at the reduced dose for the 2nd occurrence of the event Permanent discontinue for the 3rd occurrence of the event
toxicity	Grade 3 febrile neutropenia	Immediate interruption of AZD4205 Once toxicity has resolved to recovery to ≤ Grade 2 or baseline within 14 days of onset: Resume at the reduced dose for the 1st occurrence of the event, unless the toxicity can be safely and reliably controlled to ≤ Grade 2 or baseline with appropriate treatment, (dose may restart at 150 mg once daily after reaching an agreement with the sponsor). If the same non-hematological toxicity requiring dose interruption occurs again, AZD4205 should be permanently discontinued.
	Grade 3 thrombocytopenia with significant bleeding Other Grade 4 or unmanageable hematological toxicity(ies)	Permanent discontinuation Immediate interruption of AZD4205

		Once toxicity has resolved to recovery to \leq Grade 2 or baseline within 14 days of onset:
		Resume at the same dose for the 1st occurrence of the event
		 Resume at the reduced dose for the 2nd occurrence of the event
		 Permanent discontinue for the 3rd occurrence of the event
	QTcF > 500 ms absolute or > 60 ms increase from baseline	Permanent discontinuation

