	QT prolongation (QTcF > 450 ms) with signs/symptoms of life-threatening arrhythmia	Permanent discontinuation
	Confirmed drug-induced pneumonitis (any grade, see Figure 3)	Permanent discontinuation
	Grade 4 non-hematological toxicity	Permanent discontinuation
		Immediate interruption of AZD4205
Non-		Once toxicity has resolved to recovery to \leq Grade 2 or baseline within 21 days of onset:
hematological	Grade 3 Herpes Zoster	 Resume at the same dose for the 1st occurrence of the event
toxicity		 Resume at the reduced dose for the 2nd occurrence of the event
		 Permanent discontinue for the 3rd occurrence of the event
		Immediate interruption of AZD4205
		Once toxicity has resolved to recovery to \leq Grade 2 or baseline within 14 days of onset:
	Other Grade 3 or unmanageable non-hematological toxicity(ies)	Resume at the reduced dose for the 1st occurrence of the event, unless the toxicity can be safely and reliably controlled to \(\leq \text{Grade 2} \) or baseline
		with appropriate treatment, (toose may restait at 150 mg once daily after reaching an agreement with the sponsor).
		■ If the same non-hematological toxicity requiring dose interruption occurs again, AZD4205 should be permanently discontinued.

The reduced dose level of AZD4205 refers to 75 mg once daily. Patient should discontinue the study treatment, if he/she is already at the reduced dose level (75 mg) and requiring a further dose reduction due to toxicity according to the modification plan (as defined in Table 1).

If medically appropriate, Grade 4 abnormalities of hematology parameters which are considered to be of clinical concern may be repeated/confirmed within 7 days and followed up as appropriate. Supportive care such as transfusion and/or growth factor could be given per institutional guideline.

Supportive care for the management of the toxicities may be given to the patients as required in accordance with local practice/guidelines. Patients should permanently discontinue the study treatment, if the toxicities leading to interruption do not recover to ≤ Grade 2 or baseline within the maximum duration of dose interruption defined in Table 1. Patients with toxicities leading to dose discontinuation should be followed up until Grade 1 or baseline. Deviations from above guidelines may occur based on the clinical judgment of the Investigator with reaching agreement with the Medical Monitor/Sponsor.

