5.2.3 Overall benefit-risk and ethical assessment

For PTCL patients who have progressed on or are refractory/intolerant to standard treatment, the prognosis is very poor as there is no effective treatment available. This study aims to evaluate a JAK1 inhibitor, AZD4205, which potentially provides benefit to this

population with high unmet medical need, as JAK/STAT pathway has been documented to be associated with disease biology. In addition, the selectivity profile of AZD4205 against other JAK family members might provide a better tolerability profiles in clinic. Moreover, the longer half-life of AZD4205, compared with other JAK inhibitors, could potentially achieve longer duration of inhibition of JAK/STAT pathway, and thus drives better clinical activity.

The starting dose of AZD4205 is selected based on non-clinical toxicity findings as well as clinical data derived from the completed study of AZD4205 in EGFRm advanced NSCLC in Australia. The selected doses of 150 mg and 250 mg once daily are predicted to achieve biologically effective exposure and thus potentially derive clinical benefit to patients with PTCL.

Preliminary safety data at 150 mg and 250 mg suggests AZD4205 was tolerated at both doses. The most common \geq grade 3 drug related TEAEs (defined as incidence rate \geq 5%) included thrombocytopenia, neutropenia and pneumonia. The majority of TEAEs were manageable and reversible. These findings were consistent with the predicted safety risks of AZD4205. The current safety monitoring and management plan in Part A could identify these safety risks, and thus will be applied in the pivotal study (Part B).

Therefore, the benefit/risk assessment for this phase I/II study appears to be acceptable.

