5.3.1 Procedures for discontinuation of a patient from investigational product

Patients may be discontinued from investigational product in the following situations:

- Patient decision. The patient is at any time free to withdraw his/her participation in the study, without prejudice.
- Adverse events (see Table 1).
- Initiation of further line(s) of anti-cancer treatment (including bone marrow transplantation).
- Severe non-compliance to this protocol as judged by the investigator and/or Study Team.
- Disease progression as per 2014 Lugano classification, unless, in the opinion of the investigator, the patient is still deriving clinical benefit.
- Patients incorrectly initiated on investigational product (Section 5.3.2).
- Patient achieved a satisfying response confirmed for 1 year by PET or CT assessment (Section 5.1.4).
- Treatment duration reaching 2 years (approximately 35 cycles) (Section 5.1.4).

• Pregnancy.

Once study medication is permanently discontinued it cannot be restarted.

Any patient who discontinues study treatment for reasons other than disease progression should have response assessment performed as scheduled in the protocol until disease progression is documented or death occurs, unless consent is withdrawn. Study procedure related SAEs and anti-cancer treatment must be captured until the patient no longer has response assessments (disease progression or permanent withdrawal from the study).

After the final database lock, there may be some patients remaining on study treatment. For these patients, sponsor will collect information during the treatment period and for 28 days (\pm 7 days) after last dose on SAEs, death (including those due to disease progression), discontinuation due to AEs/SAEs and drug accountability.

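### In Table 1, the recurrence rule for Grade 3 febrile neutropenia names a non-hematological toxicity, so read literally it leaves open what to do after timely recovery from a second episode

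*Protocol*

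**What the plan says.** Table 1 in protocol Section 5.1.3.1 sets the dosing action for each toxicity at least possibly related to AZD4205. Grade 3 febrile neutropenia stands in the hematological block. The definition of DLT-like events in Section 5.1.1.1 classes it the same way, listing "Febrile neutropenia" under hematological toxicity.

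The row has three parts:

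- AZD4205 is interrupted immediately. This instruction is not tied to an occurrence number.
- After recovery to Grade 2 or lower, or to baseline, within 14 days: "Resume at the reduced dose for the 1st occurrence of the event, unless the toxicity can be safely and reliably controlled". In that excepted case the patient may restart at 150 mg once daily with the sponsor's agreement.
- On recurrence: "If the same non-hematological toxicity requiring dose interruption occurs again, AZD4205 should be permanently discontinued".

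The same recurrence sentence closes the row for other Grade 3 or unmanageable non-hematological toxicity, where it fits. The neighbouring ANC, platelet and other Grade 4 hematological rows instead list actions for the 1st, 2nd and 3rd occurrence, ending with "Permanent discontinue for the 3rd occurrence of the event".

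Two general rules stand below the table. A patient must stop "if he/she is already at the reduced dose level (75 mg) and requiring a further dose reduction due to toxicity" under the table's plan. A patient must also stop if the toxicity does not recover within the row's maximum interruption. For discontinuation because of adverse events, Section 5.3.1 refers back to Table 1.

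**The concern.** The recurrence sentence names a class of toxicity to which febrile neutropenia does not belong in this protocol. It looks like text carried over from the non-hematological row, because the 1st-occurrence rule and the 150 mg exception also match that row. Taken at its word, the sentence is never triggered by a second febrile neutropenia episode, and the row has nothing else to say about dosing after recovery from one.

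Table 1 is the rule that sites apply, so the risk is uneven handling. Most sites will see the intent and stop. A site that reads literally may look for another row that fits. A febrile episode with ANC below 0.5 × 10⁹/L also meets the ANC row, which permits resumption. The patient could then be re-exposed after a second febrile neutropenia episode, which the febrile neutropenia row evidently means to prevent. Discontinuations related to TEAEs also count toward the 19.7% review trigger for Part B (Section 5.1.2), which is a further reason for sites to apply one rule.

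**Working it through.** No figure in the plan is at issue and no formula applies. The check sets the rows side by side and then follows a patient through a second episode.

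**Step 1: rows of Table 1.** There are 11. Five require permanent discontinuation at the first event: Grade 3 thrombocytopenia with significant bleeding; QTcF above 500 ms or more than 60 ms over baseline; QT prolongation with signs of life-threatening arrhythmia; confirmed drug-induced pneumonitis; and Grade 4 non-hematological toxicity. The other 11 − 5 = 6 allow resumption:

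| Row | Block | Recurrence rule | Fits its own event? |
|---|---|---|---|
| ANC < 0.5 × 10⁹/L | Hematological | 1st, 2nd, 3rd occurrence listed | Yes |
| Platelets < 25 × 10⁹/L | Hematological | 1st, 2nd, 3rd occurrence listed | Yes |
| Grade 3 febrile neutropenia | Hematological | Same *non-hematological* toxicity | No |
| Other Grade 4 or unmanageable hematological | Hematological | 1st, 2nd, 3rd occurrence listed | Yes |
| Grade 3 herpes zoster | Non-hematological | 1st, 2nd, 3rd occurrence listed | Yes |
| Other Grade 3 or unmanageable non-hematological | Non-hematological | Same *non-hematological* toxicity | Yes |

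So 5 of 6 recurrence rules apply as written and 1 of 6 does not.

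**Step 2: a second febrile neutropenia episode, read literally.**

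- At onset, AZD4205 is interrupted. This is stated in the row and applies to any episode.
- With no recovery within 14 days, treatment stops permanently under the text below the table.
- With recovery within 14 days, the resume rule does not apply because it is limited to the 1st occurrence. The stop rule does not apply because it names a non-hematological toxicity. The row states no action.

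**Step 3: whether other text fills that last case.**

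- Section 5.3.1 points back to Table 1 and adds no rule.
- The 75 mg floor rule needs a patient who is already at 75 mg and whose plan requires a further reduction. The febrile neutropenia row requires none on recurrence. A patient restarted at 150 mg with the sponsor's agreement is not at 75 mg at all.
- The deviation clauses allow departures on clinical judgment with sponsor notification or agreement. They do not supply the missing rule.
- Unacceptable toxicity is a general ground for ending treatment (for example in Section 5.1.2), but it does not say that a second episode from which the patient has recovered meets it.

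**Step 4: what the ANC row would then allow.** Suppose the second episode also has ANC below 0.5 × 10⁹/L and recovers in time:

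| Dose after first episode | ANC criterion met at both episodes (2nd ANC occurrence) | ANC criterion met only at the second (1st ANC occurrence) |
|---|---|---|
| 150 mg, with sponsor agreement | Resume at 75 mg | Resume at 150 mg |
| 75 mg | Reduction called for at 75 mg; the floor rule arguably stops treatment | Resume at 75 mg |

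In three of the four cells a literal reader who turns to the ANC row resumes dosing. The cells are not weighted by how often they would occur, because the documents do not say.

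**The case against.** The strongest reply is that the intent is plain. The sentence sits inside the febrile neutropenia cell, directly after that event's 1st-occurrence rule, so a toxicity that occurs again can hardly be anything else. On that natural reading there is no gap, and the same reading lets the febrile neutropenia row prevail over the ANC row. Table 1 is described as guidance, and a site in doubt can consult the sponsor. This stands as to intent, and it keeps the point small. It does not make the wording right: an operative dosing rule should not depend on the site disregarding one of its words.

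A reader might also infer that the protocol gives no action at all for a second febrile neutropenia episode. The documents do not support that. Immediate interruption covers every episode, and the 14-day limit forces discontinuation without recovery. Only the step after timely recovery is left open. The floor rule gives some further cover, but only for a patient at 75 mg for whom the ANC row calls for another reduction.

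A reader might also take the preliminary safety data in Section 5.2.3 as showing that the situation will be common. The drug-related TEAEs of Grade 3 or higher with incidence of at least 5% "included thrombocytopenia, neutropenia and pneumonia", but nothing there says how many neutropenia cases were febrile or recurred.

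**Conclusion.** The point holds as a minor wording correction to an operative safety rule. The defect is one adjective in 1 of the 6 rows that allow resumption. Its literal effect is limited to patients who recover within 14 days from a second Grade 3 febrile neutropenia episode. For them the row does not say whether to resume, reduce or discontinue, and the ANC row can point toward resumption.

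It is not a design flaw or an absent safety rule, since the intended action is clear and the protections before recovery work as written. The number of patients affected cannot be estimated from the documents and may be small. The conclusion rests on two things: that febrile neutropenia is hematological in this protocol, which Table 1 and Section 5.1.1.1 both show, and that permanent discontinuation on recurrence is what the sponsor means, which the placement of the sentence strongly suggests. Sample size and the primary ORR analysis do not depend on it.

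**What to change.** In the Grade 3 febrile neutropenia row of Table 1, replace *the same non-hematological toxicity* with *febrile neutropenia* and leave the rest of the sentence as it is. Leave the identical sentence in the other Grade 3 non-hematological row unchanged. Add a short note to the table that the febrile neutropenia row governs when an episode also meets ANC below 0.5 × 10⁹/L.

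The cost is one phrase and one note, which can go into the next amendment or a clarification letter to sites. No change to the SAP, the sample size or the ORR analysis is needed.

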- For SAEs other variables will be collected including treatment given for the event.

It is important to distinguish between serious and severe AEs. Severity is a measure of intensity whereas seriousness is defined by the criteria in Section 6.5.2. An AE of severe intensity need not necessarily be considered serious. For example, nausea that persists for several hours may be considered severe nausea, but not a SAE. On the other hand, a stroke that results in only a limited degree of disability may be considered a mild stroke but would be a SAE.

The grading scales found in the current National Cancer Institute CTCAE version will be utilized for all events with an assigned CTCAE grading. For those events without assigned CTCAE grades, the recommendation in the CTCAE criteria that converts mild, moderate and severe events into CTCAE grades should be used. A copy of the current CTCAE version can be downloaded from the Cancer Therapy Evaluation Program website (http://ctep.cancer.gov).

Causality collection

The investigator will assess causal relationship between investigational product and each adverse event, and answer 'yes' or 'no' to the question: 'Do you consider that there is a reasonable possibility that the event may have been caused by the investigational product?'

For SAEs causal relationship will also be assessed for other medication and study procedure. Note that for SAEs that could be associated with any study procedure the causal relationship is implied as 'yes'.

A guide to the interpretation of the causality question is found in Appendix IV of this Clinical Study Protocol.

Adverse events based on signs and symptoms

All AEs spontaneously reported by the patient or care provider or reported in response to the open question from the study personnel: 'Have you had any health problems since the previous visit/you were last asked?', or revealed by observation will be collected and recorded in the CRF. When collecting AEs, the recording of diagnoses is preferred (when possible) other than recording of a list of signs and symptoms. However, if a diagnosis is known and there are other signs or symptoms that are not generally part of the diagnosis, the diagnosis and each sign or symptom will be recorded separately.

Adverse events based on examinations and tests

The criteria for determining whether an abnormal examination finding, or laboratory parameter should be reported as an adverse event are as follows:

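### The dose rule is milder for the deeper platelet fall: significant bleeding forces a permanent stop at Grade 3 thrombocytopenia but not at platelets below 25 × 10⁹/L

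*Protocol*

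**What the plan says.** Table 1 in Protocol Section 5.1.3.1 applies "If a patient has a treatment emergent adverse event (TEAE) at least possibly related to AZD4205". Four of its entries matter here.

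- **Bleeding row.** "Grade 3 thrombocytopenia with significant bleeding" leads to permanent discontinuation, with no route back to treatment.
- **Platelet-count row.** Platelets below 25 × 10⁹/L lead to immediate interruption. Bleeding is not mentioned. The patient must recover to Grade 2 or lower, or to "baseline within 21 days of onset: Resume at the same dose for the 1st occurrence of the event"; a second episode leads to the reduced dose and a third to a permanent stop.
- **Residual haematological row.** Other Grade 4 or unmanageable haematological events, again without reference to bleeding, also allow the same dose after a first recovery, here within 14 days.
- **Febrile neutropenia row.** This is a haematological row labelled Grade 3, yet its recurrence rule reads: "If the same non-hematological toxicity requiring dose interruption occurs again, AZD4205 should be permanently discontinued".

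The reduced dose is 75 mg once daily. The table is not absolute: "Deviations from these guidelines may occur based on the clinical judgment of the investigator with notification to the Sponsor". A later paragraph of the same section repeats the allowance but asks for agreement with the medical monitor or sponsor.

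**The concern.** A low platelet count with significant bleeding is more dangerous the lower the count, so the stopping rule should be at least as strict there. Table 1 does the reverse. A site that follows it literally stops the Grade 3 patient who bleeds for good, and may restart a patient with a deeper fall who bleeds at the full 150 mg.

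The thrombocytopenia rows are likely to be used. Protocol Section 5.2.3 lists thrombocytopenia among the most common drug-related events of Grade 3 or higher, defined there as an incidence of at least 5%, in preliminary data at 150 mg and 250 mg. What is at stake is patient safety and consistent handling across sites, not the primary analysis.

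**Working it through.** There is no planned figure to reproduce. The check sets the rows side by side.

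**1. Does a bare Grade 3 include Grade 4?** Elsewhere the protocol marks a minimum or a range when it means one. The DLT-like definition in Section 5.1.1.1 uses a greater-than-or-equal sign for the lung-function grade, an at-least form for Grade 4 haematological toxicity, and names Grades 3 and 4 together for non-haematological toxicity. The bleeding row does none of these, so a minimum grade cannot be assumed.

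**2. Where does a count below 25 × 10⁹/L sit?** The documents do not print the CTCAE platelet cut-offs. Table 1 gives this count a named row and then lists *other* Grade 4 events, which suggests that rows above already cover Grade 4. If the count were instead read as Grade 3, a patient with that count who bleeds would meet two rows with opposite defaults and no stated precedence. Either reading needs the same correction.

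**3. Does recording the bleed separately close the gap?** Section 6.5.3 says that for signs or symptoms outside the usual picture of a diagnosis, "the diagnosis and each sign or symptom will be recorded separately". It also makes a sign or symptom linked to an abnormal laboratory value the reported event. A bleed is therefore likely to enter the non-haematological rows too. There, "Grade 4 non-hematological toxicity" means a permanent stop. A Grade 3 or unmanageable event means interruption and then 75 mg, or 150 mg if it can be controlled and the sponsor agrees. A significant bleed below Grade 3 that is manageable meets no mandatory stop.

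**4. Defaults after a first event, patient on 150 mg, recovery in time**

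| Bleed | Grade 3 thrombocytopenia | Platelets < 25 × 10⁹/L, bleed recorded separately | Platelets < 25 × 10⁹/L, platelet row only |
|---|---|---|---|
| Grade 4 | stop | stop | 150 mg |
| Grade 3 or unmanageable | stop | 75 mg (150 mg with sponsor agreement) | 150 mg |
| Significant, manageable, below Grade 3 | stop | 150 mg | 150 mg |

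Mandatory stops: 3 of 3, 1 of 3 and 0 of 3. The three bleed classes are a device for reading the table, not categories the protocol defines.

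**5. Do other sections supply the stop?** The adverse-event reason for discontinuation in Section 5.3.1 refers back to Table 1. Unacceptable toxicity (Sections 3.1.3, 5.1 and 5.1.2) and investigator discretion (Section 5.1) allow a stop but do not require one.

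**6. Background frequency.** At the 5% floor in Section 5.2.3, 0.05 × 100 = 5 Part B patients would have drug-related thrombocytopenia of Grade 3 or higher. This assumes that the preliminary rate across both doses carries over; the 150 mg rate is not given and may be lower. It counts all such thrombocytopenia, not cases with significant bleeding, for which no rate is given.

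**7. Febrile neutropenia row.** As labelled, a Grade 4 event falls outside this row and into the residual Grade 4 row, which allows the same dose after a first recovery. The Grade 3 row defaults to the reduced dose. This is the same kind of inversion.

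**The case against.** The strongest reply is that the harmful reading is unlikely. An investigator who sees a permanent stop for the Grade 3 bleed would hardly restart full dose after a deeper fall with bleeding. The section describes its rules as guidelines and permits deviation. Interruption is immediate, and failure to recover in time already means a permanent stop. Patients who cannot come off anticoagulants or anti-platelet agents, and those with active bleeding diatheses, are excluded (Section 4.2). All of this is true and lowers the risk. But these routes rely on judgment, and a safety stop should not depend on departing from the table that defines it.

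It can also be said that the rank of the below-25 count is inferred, and that if it were Grade 3 the more specific bleeding row would naturally govern. That is a sensible reading, but no precedence is written.

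Three limits stand. *Significant* is not defined: if it means Grade 3 or worse, the class that reaches 150 mg outright disappears, although the 75 mg default for a Grade 3 bleed remains. The platelet-row-only column is less likely than separate recording. The documents do not state how many patients remain on treatment under this amendment.

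Finally, the bleeding row and the residual Grade 4 row run together in the machine-read text. The resume steps can only follow the interruption, so the permanent stop belongs to the bleeding row. Nothing suggests that a greater-than-or-equal sign was lost.

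**Conclusion.** The concern holds. Followed exactly, Table 1 sets a milder default for the deeper platelet fall with bleeding, and no text overrides it. This is an incorrect safety rule, not a missing detail, and should be corrected. The conclusion rests on the literal wording and on the absence of a precedence rule; it needs neither the CTCAE cut-offs nor the 5% figure. The size can be stated only as a difference in default action, because the event rate is not given.

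**What to change.** In Table 1:

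1. Change the bleeding row to *thrombocytopenia of Grade 3 or higher accompanied by significant bleeding*, keeping permanent discontinuation.
2. Add *without significant bleeding* to the row for platelets below 25 × 10⁹/L.
3. State that when an event meets more than one row, the most restrictive applicable row governs.
4. As a secondary correction, label the febrile neutropenia row *Grade 3 or higher* and have its recurrence rule name febrile neutropenia in place of the copied non-haematological wording.

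A footnote giving the intended bleed grade would help, but the fix works without it. Because the precedence rule reaches every row, the sponsor should read the whole table against it once before filing.

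The cost is a small protocol amendment with ethics committee and applicable regulatory approval (Section 10), which can be bundled with the next one. It adds no visits, tests or patients.
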